#### 14.3. Analysis Populations

#### **Safety Population:**

All subjects who were administered any test article excluding subjects who drop out prior to administering any test article. At least one observation should be recorded.

## **Per-Protocol Population:**

All subjects who have successfully completed all visits and did not substantially deviate from the protocol as determined by the trial cohort review committee prior to database hard lock (Per-Protocol Population). Justification of excluding subjects with protocol deviations in the Per-Protocol Population set will be documented in a memo to file.

## **Intent-to-Treat (ITT) Population:**

All randomized subjects regardless of actual treatment and subsequent withdrawal from study or deviation from protocol. At least one observation should be recorded.

## 14.4. Level of Statistical Significance

All planned analysis for this study will be conducted with an overall type I error rate of 5%. Both adjusted and unadjusted confidence intervals will be reported. For the adjustment of multiple comparisons, a Bonferroni approach will be used.

## 14.5. Primary Analysis

The primary analysis will be conducted on the Per-Protocol Population. If subject dropout rate exceeds 15%, a sensitivity analysis will be conducted on the Safety Population.

## Distance Monocular Visual Acuity (logMAR)

Distance monocular visual acuity will be analyzed using a linear mixed model post lens fitting. Sequence of lens wear, lens, period, lighting condition and the interaction between lens by lighting condition will be included in the model as fixed effects. Other baseline characteristics such as age, gender and race may be included in the model when necessary. Subject and eye nested within subject will be included as random effects. Residual errors from measurements between lighting conditions within the same period will be model using one of the following covariance structures:

- Unstructured (UN)
- Compound Symmetry (CS)
- Heterogenous Compound Symmetry (CSH)

The structure that returns the lowest finite sample corrected Akaike's Information criterion will be selected as the structure that best fits the model. The Kenward and Roger method will be used for the denominator degrees of freedom.

Comparisons between the Test and Control post lens fitting will be carried out separately for each lighting condition using 2-sided 95% confidence intervals for the least-square mean (LSM) difference (Test minus Control). Adjustments for multiple comparisons will be conducted using a Bonferroni approach.

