#### 2.3. Hypotheses

**Primary Hypotheses** 

Both primary hypotheses must be met in order to satisfy the objective of the study.

- 1. The Test lens will be non-inferior to the Control lens with respect to high luminance low contrast Distance Monocular Visual Acuity (logMAR) post lens fitting. A non-inferiority margin of 0.05 logMAR will be used.
- 2. The Test lens will be non-inferior to the Control lens with respect to low luminance high contrast Distance Monocular Visual Acuity (logMAR) post lens fitting. A non-inferiority margin of 0.05 logMAR will be used.

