#### 4. STUDY DESIGN AND RATIONALE

#### 4.1. Description of Study Design

This is a single-visit, bilateral, randomized, controlled, 2 (lens)  $\times$  2 (period) crossover, non-dispensing study. Up to 40 subjects will be enrolled with the target of approximately 34 to complete the study.

If a subject meets all eligibility criteria, they will be randomized to one of two lens wear sequences (Test/Control or Control/Test) in a bilateral fashion; otherwise they will be screen failed. Subjects will not be masked to the variant/pattern of the lenses due to visible differences in the study lenses; however, subjects will be masked to the lens brands. There will be a 5-minute washout period between study lenses.

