1.15	Subjective Best Sphere Over Refraction	Perform subjective best sphere refraction over the study lenses with a phoropter (adopt the maximum plus to maximum visual acuity (MPMVA) approach and use the duo-chrome test for binocular balancing) and record the best corrected distance visual acuity to the nearest letter (OD, OS, OU).		
1.16	Lens Power Modification (if applicable)	Adjust the lens power if the subject's best sphere over-refraction is not plano. For each power modification, repeat steps (1.13 to 1.16). Only two power modifications per eye are allowed.		
1.17	Subject Reported Ocular Symptoms	Subjects will respond to a verbal open-ended symptoms questionnaire.		
1.18	Distance ETDRS LogMAR Visual Acuity-	Per please confirm room illuminance and chart luminance acceptable ranges for both high/low contrast visual acuity testing.		

		1. Under high illumination and high chart	
		luminance, record the distance (4 meter) ETDRS high contrast visual acuity OD (HC1), OS (HC2) and OU (HC3).	
		2. Under high illumination and high chart luminance, record the distance (4 meter) ETDRS low contrast visual acuity OD (LC1), OS (LC2), and OU (LC3).	
		3. With the goggles on, under high illumination and chart luminance, record the distance (4 meter) ETDRS high contrast visual acuity OD (HC1), OS (HC2) and OU (HC3). Allow subject to adjust to dim condition for 3 minutes	
		Letter-by-letter results will be recorded into the electronic data capture form, which will calculate the visual performance score for each chart read.	
1.19	Cosmetic Lens Fit Assessment (without slit-lamp)	The Cosmetic Lens Assessment will be assessed by the investigator (without slit-lamp) in primary gaze and extreme gaze (right, left, and upgaze) at a normal conversation distance (approximately three (3) feet away from the subject).	Appendix E
1.20	Hula Hoop Assessment (without slit-lamp) *if unacceptable cosmetic lens fit in any gaze*	If there is an unacceptable cosmetic fit in any gaze, the Hula Hoop Assessment will be assessed by the investigator (without slit-lamp) in primary gaze and extreme gaze (right, left, and upgaze) at a normal conversation distance (approximately three (3) feet away from the subject).	Appendix E
1.21	Subjective Lens Fit Assessment	Evaluate overall lens fit acceptance (acceptable or unacceptable) based on centration, movement and other fitting characteristics.	

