#### 14. STATISTICAL METHODS

#### 14.1. General Considerations

Statistical Analysis will be undertaken by the sponsor or under the authority of the sponsor. A general description of the statistical methods to be implemented in this clinical trial is outlined below. All data summaries and statistical analyses will be performed using the SAS software Version 9.4 or higher (SAS Institute, Cary, NC). Throughout the analysis of data, the results for each subject/eye will be used when available for summarization and statistical analysis. Unscheduled visits will be summarized separately and will be excluded from the statistical analysis.

Summary tables (descriptive statistics and/or frequency tables) will be provided for all baseline variables, efficacy variables and safety variables as appropriate. Continuous variables will be summarized with descriptive statistics (n, mean, standard deviation [SD], median, minimum and maximum). Frequency count and percentage of subjects or eyes within each category will be provided for categorical data.

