#### 14.2. Sample Size Justification

This study was designed and powered to test for non-inferiority of the Test relative to the Control with respect to Distance Monocular Visual Acuity (logMAR) post lens fitting under the lighting conditions, low luminance high contrast and high luminance low contrast. Historical data from was utilized for the sample size calculation since this study used the same control lens (1-Day Acuvue Define Vivid Style). Was a dispensing, 4-visit, 2×2 crossover where, 313 subjects were enrolled with 282 completing the study. However, visual acuity was only collected post lens fitting. Table 4 below contains the summary of visual acuity (logMAR) by lighting condition and lens type.

Table 4: Descriptive Summary of Distance Monocular Visual Acuity (logMAR)

Lens Type	High Luminance Low Contrast	Low Luminance High Contrast
Control -Mean	0.0474 (0.09041)	0.0851 (0.09454)
$(SD^1)$		

<sup>1SD: Standard Deviation

Since the Test and Control lenses have not been utilized in the same study, it was assumed for the sample size calculation that there was no difference between the Test and Control lenses and that both study lenses have similar variation with respect to visual acuity for both lighting conditions and that there was a perfect correlation between the left and right eyes. Furthermore, a conservative estimate of 0.30 was used for the intraclass correlation between periods, providing a sample size estimate based on the "worst-case" scenario. The sample size was calculated using a two-sided type I error rate of 5% to achieve a minimum power of 80%. The calculation was performed using the POWER Procedure in SAS Version 5.1. Table 5 below contains the sample size to test for non-inferiority of the Test relative to the Control for each lighting condition.

Table 5: Sample Size Calculation to Test for Non-Inferiority – Visual Acuity

	Minimum Number of	
Lighting Condition	Subjects to Complete	Power (%)
High Luminance Low	30	80.4
Contrast		
Low Luminance High	33	80.7
Contrast		

As shown in the table above, to meet both primary hypotheses a minimum of 33 subjects are required to complete the study. Since this is 2×2 crossover we will aim to complete 34 subjects with equal allocation between the 2 lens wear sequences. To adjust to subject dropout, approximately 40 subjects will be enrolled to ensure that at least 34 subjects complete the study.

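### The primary mixed model does not define its residual block; if the block is one eye in one period, the deciding confidence interval treats a subject's two eyes as independent and can be too narrow

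*Combined protocol and SAP*

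**What the plan says.** Section 14.5 fits one linear mixed model to monocular acuity in both lighting conditions, with fixed effects for sequence, lens, period, lighting condition and lens by lighting condition. The random part reads "Subject and eye nested within subject will be included as random effects". The rest of the covariance is given by "Residual errors from measurements between lighting conditions within the same period will be model using one of the following covariance structures", with UN, CS and CSH as the candidates, and the choice goes to "The structure that returns the lowest finite sample corrected Akaike's Information criterion". Degrees of freedom are Kenward-Roger. Non-inferiority is declared when the upper limit of each 95% interval for Test minus Control is below 0.05 logMAR. Section 2.3 adds "Both primary hypotheses must be met in order to satisfy the objective of the study".

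Three other statements concern the two eyes:
- Section 4.1 says of eligible subjects that "they will be randomized to one of two lens wear sequences (Test/Control or Control/Test) in a bilateral fashion", so both eyes wear the same lens in a period.
- Section 14.1 says "the results for each subject/eye will be used when available for summarization and statistical analysis".
- Section 14.2 sizes the trial on the assumption that "there was a perfect correlation between the left and right eyes".

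No section says whether a residual block is one eye in one period or one subject in one period, and none names a subject-by-period or subject-by-lens effect.

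**The concern.** Subject and eye-within-subject effects are constant over periods, so both drop out of Test minus Control. The standard error of the lens difference therefore depends on the residual covariance alone, and the text allows two codings.

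- **Eye-period block.** Residuals are correlated across lighting conditions within one eye and one period and are independent otherwise. A subject's two lens differences then count as independent.
- **Subject-period block.** The residual matrix covers eye by lighting condition, and the between-eye covariance is estimated.

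Anything that shifts both eyes together in a period, such as fatigue, effort or learning, makes the two lens differences correlated. The eye-period block cannot represent this, and Kenward-Roger cannot restore a covariance that the model omits. The AICc rule chooses a structure within a block and does not choose the block. The upper limit of this interval decides the trial, so two analysts following the same text could reach different conclusions.

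**Working it through.** **Inputs from section 14.2.** SD 0.09041 (high luminance low contrast) and 0.09454 (low luminance high contrast), between-period correlation 0.30, 34 completers. The margin of 0.05 is from section 2.3.

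**The plan's own figure.** With perfectly correlated eyes each subject counts once, so the SD of the difference is SD × √(2 × 0.70). A paired-t calculation at one-sided 5% reproduces Table 5 exactly: 80.4% with 30 completers and 80.7% with 33. For 34 completers and SD 0.09454 this sizing implies a standard error of 0.09454 × √1.4 / √34 = 0.0192.

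**Algebra.** Let r be the between-eye correlation of period-specific error. Because the stable effects cancel, r is also the correlation of the two eyes' lens differences.
- Eye-period block: variance = 2 × 0.70 × SD² / (2 × 34), whatever r is. For SD 0.09454, SE = 0.0136 and the 95% half-width is 0.027.
- True variance: the same figure × (1 + r). SE = 0.0136, 0.0166 and 0.0192 at r = 0, 0.5 and 1, with half-widths 0.028, 0.034 and 0.039.
- Reported/true SE = 1/√(1 + r). The one-sided error at the margin is Φ(−1.96/√(1 + r)).

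At r = 1, the plan's sizing assumption, the eye-period model would report 0.0136 where the sizing calculation used 0.0192, an understatement of 29%.

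**Simulation of the section 14.5 model.** There were 6,000 crossovers per scenario (17 per sequence), with a true difference of 0.05 and REML fits with Kenward-Roger. AICc chose between UN and CS; in a 2×2 block CSH equals UN. Variances of the subject and eye effects were bounded at zero. Assumed, because the documents do not give it: a residual correlation of 0.4 between lighting conditions, and three splits of the stable variance. Split A is all subject-level; B is half subject, half eye; C has 10% of total variance subject-by-lighting and 10% eye-by-lighting.

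Eye-period block (ranges over splits and lighting conditions):

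| r | SE ratio, formula | Error, formula | SE ratio, simulated | Error per condition, simulated | Error, Bonferroni interval | Joint error, both at margin |
|---|---|---|---|---|---|---|
| 0 | 1.00 | 2.5% | – | 2.5/2.8% (split A) | – | – |
| 0.1 | 0.95 | 3.1% | 0.92–1.02 | 2.3–3.3% | 1.3–1.8% | – |
| 0.3 | 0.88 | 4.3% | 0.83–0.93 | 3.3–5.1% | 1.7–3.0% | 0.6–0.9% |
| 0.5 | 0.82 | 5.5% | 0.75–0.84 | 5.0–6.9% | 3.2–4.7% | 1.1–1.5% |
| 0.95 | 0.72 | 8.0% | 0.62–0.70 | 8.6–11.5% | 6.0–8.5% | 2.4–3.1% |

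Monte Carlo standard errors are about 0.2 points near 2.5%, 0.3 near 6% and 0.4 near 11%. Setting the lighting correlation to 0.1 or 0.7 (split A, r = 0.5) gives 6.5/6.5% or 7.3/6.9% per condition, and joint error of 0.5% or 3.1%. Two smaller simulations agree: about 6–7% at r = 0.5 and 10–13% at r of 0.93–0.95.

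Subject-period block: 2.4–2.9% at every r with a 4×4 UN matrix, and 2.3–3.0% when AICc chooses among the three structures. Median denominator degrees of freedom at r = 0.5 are about 38 with the 4×4 matrix. With the eye-period block they are 106 (UN) or 192 (CS), far more than 34 subjects can supply.

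**The case against.** The strongest reply is that this is missing wording and not a demonstrated wrong analysis. UN and CSH coincide in a 2×2 block, so listing both makes more sense if the block is larger, which points to the subject-period block and nominal error. That hint is real but weak. The structure is indexed by lighting condition only, and a matrix so indexed cannot hold both eyes' readings. Section 7.2 also records a third acuity (high luminance, high contrast), and a 3×3 per-eye block would separate UN from CSH too.

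Second, the documents do not give r. Perfect correlation is a sizing assumption, not an estimate. Each eye is read separately and refitted separately ("Only two power modifications per eye are allowed"), which lowers r. This stands: at r = 0.1 the error is close to nominal, and unmodelled stable lighting-specific variance (split C) can offset the effect at small r.

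Third, the highest rates come mostly from split A, and simulation exceeds the formula at high r partly because the eye variance is held at or above zero. This also stands. The formula alone still gives 5.5% at r = 0.5 and 8.0% at 0.95.

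Fourth, other rules soften the effect. If the Bonferroni interval decides, error passes 2.5% only above r of about 0.3: the formula gives Φ(−2.241/√1.3) = 2.47% there, and the exact crossing depends on the split. Requiring both conditions lowers the joint error when both sit at the margin. It gives no protection when one condition passes easily.

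**Conclusion.** The concern holds in its conditional form. Section 14.5 leaves the residual block undefined, and its wording most naturally leads to the eye-period block, which contradicts the eye correlation used for sizing. On that coding, false non-inferiority per lighting condition rises from 2.5% to roughly 3–5% at r = 0.3, 5–7% at r = 0.5 and 9–12% at r = 0.95. These rates assume the unadjusted interval, one condition at the margin with the other passing easily, and the variance splits above. There is no inflation at r = 0 or with a subject-period block covering both eyes. Confidence is medium, because neither the intended block nor r can be read from the documents. The gap should be closed before unmasking, since the choice can decide the primary claim.

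**What to change.** In section 14.5, define the residual block as subject-by-period, with an unstructured 4×4 covariance over eye and lighting condition, fixed in advance. If that fit does not converge, keep the per-eye block and add a random subject-by-period effect with unstructured covariance across the two lighting conditions (simulated error 2.3–2.9%). With complete data, analysing the two-eye mean per subject, period and lighting condition also works (2.2–2.8%). Naming the subject-period block and keeping the AICc rule would hold the error too; fixing the structure also removes a data-driven choice.

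The change is one sentence and one model line, with no new data. It takes 12 covariance parameters (10 residual, 2 random) instead of 4–5. Compared with the eye-period block, the mean 95% interval from the two-eye mean is wider by 3–5% at r = 0, 11–22% at 0.3, 21–35% at 0.5 and 47–65% at 0.95. The 4×4 fit adds about 1–1.5%.

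Power with the 4×4 fit (34 completers, true difference 0, one-sided 2.5%):

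| r | High luminance low contrast | Low luminance high contrast | Both |
|---|---|---|---|
| 0 | 95% | 94% | 90% |
| 0.3 | 90% | 87% | 80% |
| 0.5 | 85% | 82% | 73% |
| 0.95 | 75% | 71% | 58% |

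The low power at high r reflects the true standard error and is not caused by the fix. Table 5 reproduces only at one-sided 5%. At the one-sided 2.5% level that the decision rule uses, 34 completers with perfectly correlated eyes give about 75% and 72%. That is a separate sizing matter.

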## **Hypothesis:**

The null and alternative hypothesis for visual acuity to test for non-inferiority of the Test lens relative to the Control lens is as follows:

$$H_o$$
:  $\mu_T - \mu_C \ge 0.05$   
 $H_A$ :  $\mu_T - \mu_C < 0.05$ 

Where  $\mu_T$  and  $\mu_C$  represent the populations means for distance monocular visual acuity for the Test and Control lenses, respectively. Non-inferiority will be tested separately for each lighting condition. Non-inferiority will be declared if the upper limit of each 95% confidence interval for the LSM difference between the Test and Control is below 0.05. i.e. P( $\mu_T - \mu_C < 0.05$ )  $\geq 0.975$ .

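### The pooled primary model has no lighting-specific subject or eye effect, so stable person-by-lighting variation mis-states the standard error behind each co-primary confidence interval

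*Combined protocol and SAP*

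**What the plan says.** Section 14.5, under Distance Monocular Visual Acuity (logMAR), specifies one linear mixed model for both lighting conditions. Besides sequence, lens and period, "lighting condition and the interaction between lens by lighting condition will be included in the model as fixed effects". On the random part it says "Subject and eye nested within subject will be included as random effects". On the residual it says "Residual errors from measurements between lighting conditions within the same period will be model using one of the following covariance structures", followed by unstructured (UN), compound symmetry (CS) and heterogeneous compound symmetry (CSH); the finite-sample corrected AIC chooses among them.

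Inference is by condition: the lens comparisons "will be carried out separately for each lighting condition using 2-sided 95% confidence intervals". Non-inferiority is declared "if the upper limit of each 95% confidence interval for the LSM difference between the Test and Control is below 0.05", and Section 2.3 adds that "Both primary hypotheses must be met in order to satisfy the objective of the study". For planning, Section 14.2 says that "a conservative estimate of 0.30 was used for the intraclass correlation between periods".

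**The concern.** The two periods are linked only by a subject intercept and an eye intercept, and neither depends on lighting. The model thus assumes that a reading in period 1 covaries equally with the period 2 reading in the same lighting condition and with the period 2 reading in the other one. A person who is reliably worse in dim light than at low contrast, relative to other subjects, breaks that assumption.

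Such a stable person-by-lighting offset is the same under both lenses, so it cancels from the Test minus Control difference within a condition and should not enter its standard error (SE). The model has no place for it except the residual, and the residual sets that SE. UN, CS and CSH describe only how the two conditions relate within a period, so none of them can carry the offset from one period to the next. The width of each interval that decides a co-primary hypothesis is at stake.

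**Working it through.** **Inputs.** SDs 0.09041 (high luminance low contrast, HLLC) and 0.09454 (low luminance high contrast, LLHC) from Table 4; intraclass correlation 0.30, margin 0.05 and 34 completers from Section 14.2. Assumptions: residual blocks are subject × eye × period (the plan does not state the block), and a share *f* of the stable variance is lighting-specific (the documents give no value).

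**1. The plan's own figure.** Table 5 follows from a paired non-inferiority t-test with one value per subject, true difference 0 and SD of the difference = SD × √[2(1 − 0.30)], that is 0.1070 and 0.1119. At one-sided 5% this gives 80.4% power with 30 subjects and 80.7% with 33, as printed. (At one-sided 2.5%, which corresponds to the 95% interval rule, the same numbers give 69.7% and 70.2%. That is a separate matter and is not used here.) This formula contains only the between-period correlation within a lighting condition.

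**2. What the model reports.** Let each reading have variance σ². Let ρs be the between-period correlation within a condition, ρx the between-period correlation across conditions, and ρw the within-period correlation across conditions. The period difference in one condition is A + B, where A is half the period difference of the sum over conditions and B is half the period difference of the between-condition difference. Let C be half the period sum of the between-condition difference.

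- Var A = σ²(1 + ρw − ρs − ρx)
- Var B = σ²(1 − ρw − ρs + ρx)
- Var C = σ²(1 − ρw + ρs − ρx)

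The true variance of A + B is 2σ²(1 − ρs). In the plan's model the intercepts drop out of the between-condition difference and residuals in different periods are independent, so Var B = Var C is forced. The fit settles on their average, σ²(1 − ρw). The reported variance becomes Var A + σ²(1 − ρw) = 2σ²[1 − (ρs + ρx)/2], so

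model SE / true SE = √{[1 − (ρs + ρx)/2] / (1 − ρs)}.

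The full two-eye model gives the same ratio when the eyes share no within-period variation.

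**3. Size of this term alone (UN).** With ρx = (1 − f)ρs:

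| ρs | f | ρx | Formula | Ratio | Two-eye model, Table 4 SDs (HLLC, LLHC) |
|---|---|---|---|---|---|
| any | 0 | ρs | 1 | 1.000 | 1.00, 1.00 |
| 0.30 | 0.25 | 0.225 | √(0.7375/0.70) | 1.026 | 1.026, 1.027 |
| 0.30 | 0.50 | 0.15 | √(0.775/0.70) | 1.052 | 1.052, 1.052 |
| 0.60 | 0.17 | 0.50 | √(0.45/0.40) | 1.061 | not run |
| 0.60 | 0.25 | 0.45 | √(0.475/0.40) | 1.090 | 1.085, 1.095 |
| 0.60 | 0.50 | 0.30 | √(0.55/0.40) | 1.173 | 1.166, 1.179 |

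In logMAR, at 0.60 and f = 0.25: mean total variance (0.09041² + 0.09454²)/2 = 0.008556 and stable part 0.60 × 0.008556 = 0.005134. The residuals are 0.008174 − 0.005134 = 0.003040 and 0.008938 − 0.005134 = 0.003804. With two eyes and 34 subjects the true SEs are √(0.003040/34) = 0.0095 and √(0.003804/34) = 0.0106. The model reports 0.0095 × 1.085 = 0.0103 and 0.0106 × 1.095 = 0.0116.

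**4. Simulation.** REML fits of the plan's model to 34 subjects (600 runs per scenario, Monte Carlo error about 0.9 points) gave 95% interval coverage (HLLC/LLHC) of 94.8%/94.5% with f = 0 at 0.60, 96.3%/96.8% with f = 0.25 and 98.5%/97.7% with f = 0.50. Paired analysis of the two-eye mean within each condition gave 94.3% to 95.0% in the same scenarios. At 0.30 with f = 0.50 the pooled figures were 94.7%/97.0%, so the smaller effect is hardly visible with this many runs.

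**5. Variation the eyes share within a period.** Let a share *g* of the within-period residual be common to both eyes. With equal variances and no stable eye effect, model SE / true SE is:

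| ρs, ρx | g | Plan's model | Separate fits, no subject-by-period | Separate fits with subject-by-period |
|---|---|---|---|---|
| 0.30, 0.15 | 0 | 1.05 | 1.00 | 1.00 |
| 0.30, 0.15 | 0.30 | 0.90 | 0.83 | 1.00 |
| 0.30, 0.15 | 0.50 | 0.83 | 0.75 | 1.00 |
| 0.30, 0.15 | 0.98 | 0.69 | 0.58 | 1.00 |
| 0.60, 0.40 | 0 | 1.12 | 1.00 | 1.00 |
| 0.60, 0.40 | 0.30 | 0.96 | 0.83 | 1.00 |
| 0.60, 0.40 | 0.50 | 0.88 | 0.75 | 1.00 |

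**6. Choice of residual structure.** With two conditions, UN and CSH are the same three-parameter model. CS forces one residual variance on both conditions. In a scenario with the Table 4 SDs and no eye sharing, the ratios (HLLC/LLHC) are 1.03/1.04 under UN and 1.06/1.01 under CS.

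**The case against.** The strongest reply is that the size is unknown, modest at the plan's own correlation, and on the safe side. Much of that stands. The documents give neither ρx nor a person-by-lighting variance; at 0.30 the effect is about 3-5% of interval width, and taken alone it does not inflate false claims of non-inferiority. Section 14.2 offers 0.30 as a low planning value, however, and for a given *f* the ratio rises with the correlation.

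Stronger readings are tempting, and the documents do not support them:

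- **A reader might infer that the trial's intervals are too wide overall.** Both eyes enter the model without a subject-by-period term, and step 5 shows that shared eye variation can make the net SE too small, for example 0.90 of its true value at 30% sharing. Nor is this term always widening: if the stable variances differ and the conditions are almost perfectly correlated, or if CS is selected, one interval can be 1-2% too narrow.
- **A reader might put the step 2 ratio through the sample-size formula and quote a loss of power or a test size.** That formula uses one value per subject, because Section 14.2 assumes perfect correlation between eyes. The model in Section 14.5 fits two eyes, and with near-perfect eye correlation its SE is too small (0.69). No power or size figure is therefore given here.
- **A reader might infer that choosing among UN, CS and CSH has no bearing on the lens SE.** It cannot repair this defect, but CS against UN or CSH does move the SE between conditions when their variances differ (step 6).
- **A reader might count the common period and sequence effects as a further error.** With equal allocation to sequences, period-by-lighting is orthogonal to the lens contrast within a condition, and no harm has been shown.

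**Conclusion.** The point holds as a mis-specified standard error. Under residual blocks of subject × eye × period, the pooled model moves stable person-by-lighting variation into the residual that sets each co-primary interval. Under UN with similar variances this term alone widens the interval by about 3-5% at an intraclass correlation of 0.30 and about 6-18% at an assumed 0.60; it is nil if there is no such variation. Alone it is conservative and costs some power. The net direction cannot be settled from the documents, because the missing subject-by-period term acts the other way and can outweigh it. The plan treats the conditions as two hypotheses with separate intervals, so the lens estimates do not need the restriction.

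**What to change.** In Section 14.5, fit the primary model separately for each lighting condition. Fixed effects: sequence, period and lens. Random effects: subject, eye within subject, and subject-by-period.

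Name the subject-by-period term explicitly. Splitting the model without it can give a narrower interval than the plan's: 0.83 against 0.90 of the true SE at 30% eye sharing in step 5. With it, the ratio was 1.00 in every scenario tried.

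Each fit then holds one lighting condition, so the selection among UN, CS and CSH is no longer needed and can be deleted. The Kenward-Roger degrees of freedom, margin and interval rule are unaffected. The cost is SAP wording and a few lines of code, with no added data, visits or subjects.
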